## 6 Study Conduct

### 6.1 Subject Disposition, Completion Rate and Reasons for Discontinuation

Subject disposition will be summarized for the Randomized Sample by the treatment group, and by center.

Subject completion rate and reasons for discontinuation will be summarized for the Randomized Sample by treatment group.

### 6.2 Treatment Compliance

Based on the Investigational medicinal product (IMP) panel of the CRF, compliance in taking IMP is calculated by dividing the number of tablets/capsules taken by the total number of tablets/capsules the patients were scheduled to take during the study period. For lost-to-follow up patients, last IMP end date record will be used as the treatment end date.

SAP 331-201-00080

### **6.3 Protocol Deviation**

Protocol deviations will be summarized by center and type of deviation for randomized subjects by treatment group. A listing of protocol deviations will be provided.

## **7 Baseline Characteristics**

### **7.1 Baseline Definition**

For analyses of the double-blind treatment period data, the baseline is the Baseline measurement (expected to be at Day 1). Baseline measurement is defined as the last available measurement prior to the start of double-blind IMP.

### **7.2 Demographic Characteristics**

Baseline demographic characteristics include age, sex, race, ethnicity, height, weight, waist circumference, and body mass index (BMI). For the Randomized Sample, demographic characteristics will be summarized by treatment group.

Mean, range and standard deviation will be used to describe continuous variables such as age. Frequency distributions will be tabulated for categorical variables such as race.

### **7.3 Medical and Psychiatric History**

A summary of medical, psychiatric, and bipolar I disorder history will be presented for the Randomized Sample (by treatment group and overall).

### **7.4 Neuropsychiatric Diagnosis**

A summary of the MINI International Neuropsychiatric Interview (M.I.N.I.) will be presented for the Randomized Sample (by treatment group and overall). Summarized will be the number and percentage of patients who meet each diagnosis criteria, and number and percentage of patients with each primary diagnosis.

### **7.5 Baseline Psychiatric Evaluation**

For the Randomized Sample, baseline psychiatric scale evaluation will be summarized by treatment group and overall. The mean, median, range and standard deviation will be used to summarize the assessments of: YMRS Total Score, Clinical Global Impression – Bipolar

SAP 331-201-00080

(CGI-BP) severity score in mania, **CCI** [REDACTED]  
[REDACTED]

## 8 Efficacy Analysis

All efficacy analyses pertaining to the double-blind treatment period will be performed on the Efficacy Sample, and patients will be included in the treatment group as randomized.

Statistical comparisons are based on 2-sided, 0.05 significance levels.

### 8.1 Primary Efficacy Endpoint

The primary efficacy endpoint is the change from baseline to Day 21 of the double-blind treatment phase in YMRS Total Score. For analysis of the double-blind treatment phase data, baseline is defined as the last available measurement prior to the first dose of double-blind IMP.

#### 8.1.1 Primary Efficacy Analysis

The objective of the primary analysis is to demonstrate the efficacy of brexpiprazole for the acute treatment of manic episodes, with or without mixed features, in subjects with a diagnosis of bipolar I disorder.

[figure not shown]
[figure not shown]
The estimand for the primary efficacy analysis is the difference in outcome improvement if all subjects tolerated and adhered to their treatment. This approach is Estimand #3 recommended by the 2010 National Academy of Sciences' National Research Council report on prevention and treatment of missing data and ICH E9 (R1) "Addendum to Statistical Principles for Clinical Trials on Choosing Appropriate Estimands and Defining Sensitivity Analyses in Clinical Trials".

This estimand focuses on the efficacy of brexpiprazole in change from the baseline in YMRS Total Score. The objective of this trial is consistent with the election of an efficacy rather than effectiveness estimand.

The primary analysis will be performed on the Efficacy Sample which includes all randomized subjects who took at least 1 dose of IMP in the double-blind treatment phase and who have both a baseline value and at least 1 post-randomization YMRS Total Score during the double-blind treatment phase. The primary efficacy analysis will be performed by fitting a mixed-effect model repeated measure (MMRM) analysis with an unstructured variance covariance structure in which the change from the baseline in YMRS Total Score during the

SAP 331-201-00080

double-blind treatment phase will be the dependent variable based on the observed cases (OC) data set. The OC data set will consist of actual observations recorded at each visit during the double-blind treatment phase and no missing data will be imputed. CCI [REDACTED]

SAP 331-201-00080

SAP 331-201-00080

1) CCI

SAP 331-201-00080

**8.1.3.2**

CCI

**8.1.4 Subgroup Analyses**

Subgroup analyses of change from baseline in YMRS Total Score to every study week in the double-blind treatment period will be performed by the following factors:

- Sex (Based on the biological status)
- Race (White and All Other Races)
- Age group (Age<55 and Age≥55)
- Region (North America and Europe)

All subgroup analyses will be conducted using the same MMRM analysis as for the primary efficacy analysis except that the fixed class effect term for trial center will not be included in the model

CCI

SAP 331-201-00080

[figure not shown]
## 8.2 Secondary Endpoint Analysis

The key secondary efficacy endpoint is the change from baseline to Day 21 in the double-blind treatment phase in CGI-BP severity of illness score in mania. This endpoint will be analyzed by fitting the similar MMRM model described in the primary analysis. In order to control the overall type I error rate, a hierarchical testing procedure will be used. If the primary efficacy analysis for the YMRS Total Score yields a statistically significant result at 0.05 (2-sided) for the comparison of brexpiprazole versus placebo, then the comparison for key secondary efficacy variable (CGI-S score) will be tested at an alpha level of 0.05 (2-sided).

CCI

SAP 331-201-00080

## 9 Safety Analysis

Standard safety variables to be analyzed include Adverse Events (AEs), clinical laboratory tests, vital signs, body weight, waist circumference, BMI, 12-lead electrocardiograms (ECGs), and physical examinations. CCI

and Columbia-Suicide Severity Rating Scale (C-SSRS).

SAP 331-201-00080

Safety analysis will be conducted based on the Safety Sample unless indicated otherwise. In general, baseline of a safety variable is defined as the last observation of the variable before taking the first dose of IMP, unless specified otherwise. Prospectively defined criteria will be used to identify potentially clinically relevant abnormal values for clinical laboratory tests, vital signs, ECGs, and body weight.

### 9.1 Adverse Events

All adverse events will be coded by System Organ Class (SOC) and Preferred Term (PT) according to the Medical Dictionary for Regulatory Activities (MedDRA). AEs that are sex-specific, e.g., ovarian cancer, will have their incidence rates evaluated for the specific sex.

Treatment-emergent AEs (TEAEs) are defined as AEs with an onset date on or after the start of double-blind treatment period. In more detail, TEAEs are all adverse events which started after start of double blind IMP; or if the event was continuous from baseline and was worsening, serious, study drug related, or resulted in death, discontinuation, interruption or reduction of study therapy. Adverse events occurring up to 30 days after the last day of IMP will be included in the summary tables.

The incidence of the following events in the double-blind treatment period will be tabulated by treatment group and overall using the Safety Sample:

- a) TEAEs
- b) TEAEs by severity
- c) TEAEs potentially causally related to the IMP
- d) TEAEs with an outcome of death
- e) Serious TEAEs
- f) TEAEs leading to discontinuations of the IMP

The above summaries (b), (e) and (f) will also be prepared for TEAEs potentially causally related to the IMP.

In addition, incidence of TEAE during the double-blind treatment period of at least 5% in any treatment group other than placebo group, and also greater than placebo by SOC and PT will be provided.

Incidence of TEAEs by SOC and PT will be summarized for sex, race, age and region subgroups.

CCI

SAP 331-201-00080

CCl

Unless otherwise specified, in general, analysis of safety data will be performed on observed case and for last visit.

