^aScreening begins when the ICF is signed and will take place between Day -14 and Day -1; however, screening procedures should be initiated with a sufficient amount of time allotted in order to obtain laboratory results and ECG results from the central reader prior to randomization. Review of inclusion/exclusion criteria at baseline will be based on assessments performed during screening. Hospitalization will begin with the signing of the ICF for subjects who are not already hospitalized at the initial screening visit. Note: In the rare circumstance when a subject must leave the inpatient facility temporarily (eg, family emergency or doctor visit), a temporary day pass may be granted. For such a request, sites must first contact the medical monitor for explicit authorization and guidance on procedures. A medical monitor approved day pass is good for the day requested only, and subjects must return to the site the same day (eg, in the evening).

^bIf a subject discontinues prematurely before Day 21, procedures noted for Day 21 must be completed at the ET visit.

^cConsists of telephone contact or clinic visit (investigator's discretion) for evaluation of safety 21 days after the last dose of IMP and applies only to subjects who do not enter the optional open-label rollover trial.

^dInformed consent must be obtained prior to any trial-related procedures. CCI [REDACTED]

^eAll medications taken within 30 days of screening will be recorded. In addition, all prescription and non-prescription medications taken during the trial will be recorded as concomitant medications.

^fTo be eligible for the trial, subjects must have a YMRS score ≥ 24 at screening and baseline.

CCI [REDACTED]

^hTo include measurement of height at screening only and waist circumference at screening and Day 21.

ⁱVital signs include body weight, body temperature, systolic blood pressure (SBP), diastolic blood pressure (DBP), and heart rate. Blood pressure and heart rate will be measured in the following order: supine and standing after the subject has been in each position for at least 3 minutes. Vital signs scheduled for the same visit as blood samples are to be completed before blood is drawn.

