3.7.1.8 Post-treatment Follow-up Period

Subjects will be contacted for a safety follow-up either via telephone or in-clinic visit (at the investigator's discretion) scheduled 21 (\pm 2) days after the last dose of IMP. Adverse events and concomitant medications will be recorded. This contact also applies to subjects withdrawn prematurely from the trial.

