## 10 Conventions

### 10.1 Study Visit Windows

Study visit windows will be used to map visits using study day intervals. Observations at each scheduled visit and Early Termination will be assigned to Day 4, Day 7, Day 14 and Day 21 visits based on their visit windows as shown in [Table 10.1A](#). This visit window convention applies to tables and listings for all efficacy and safety scales (YMRS, CGI-BP, [CCI](#) [REDACTED] [REDACTED]). This derived study window variable will be named as DAY and will be footnoted. In listings, it will be listed along with the CRF study visit.

[Table 10.1A](#) shows classifications for study day intervals in the double-blind period. The variable “target day” is defined using the number of days since the start of double-blind dosing. The first day of double-blind dosing is defined as “Day 1”.

[figure not shown]
If more than one observation falls within a particular study day interval, then the last observation within that interval is used. Evaluations occurring more than 7 days after the last double-blind dosing date will not be mapped into study visit windows, and will be excluded from the analysis.

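### Does counting adverse events for 30 days after the last dose, in tables labelled as double-blind, spoil the safety comparison between the arms?

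*SAP*

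**What the plan says.** SAP 9.1 gives treatment-emergent events a start: "Treatment-emergent AEs (TEAEs) are defined as AEs with an onset date on or after the start of double-blind treatment period". The only end point in the readable text is the inclusion rule: "Adverse events occurring up to 30 days after the last day of IMP will be included in the summary tables". The tables are then introduced with "The incidence of the following events in the double-blind treatment period will be tabulated by treatment group and overall using the Safety Sample". The common-event table carries the same label: "incidence of TEAE during the double-blind treatment period of at least 5% in any treatment group other than placebo group", and greater than placebo.

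The protocol (Synopsis and section 3.7) makes the double-blind period 3 weeks and lists follow-up separately. The one planned safety contact after dosing is 21 (±2) days after the last dose. Footnote c of the Schedule of Assessments says it "applies only to subjects who do not enter the optional open-label rollover trial". Protocol 3.7.1.8 describes the same contact without that limit: "Adverse events and concomitant medications will be recorded. This contact also applies to subjects withdrawn prematurely from the trial".

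Two other SAP sections treat post-dose time differently. Section 10.1 says of scale ratings: "Evaluations occurring more than 7 days after the last double-blind dosing date will not be mapped into study visit windows". Section 9.8 tabulates concomitant medications separately for before, during and after study therapy.

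**The concern.** The label says double-blind, but most of the nominal window lies after double-blind drug. If completers start open-label treatment straight after Day 21 and their events reach these tables, a placebo subject's event on open-label drug would be counted under placebo. That would pull the arms together. If those events do not reach the tables, rollover subjects have almost no post-dose observation while the others have about three weeks. Rollover depends on completing Day 21, which may differ by arm.

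Safety and tolerability is the trial's secondary objective, and by-arm incidence decides which events enter the table of at least 5% and greater than placebo. The SAP limits post-dose time for rating scales and splits it for concomitant medications, so the adverse-event section looks like an oversight.

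**Working it through.** **The plan's own duration.** Screening up to 14 days, treatment 21 days, contact at 21 days: 14 + 21 + 21 = 56 days = 8.0 weeks, matching the stated figure of approximately 8 weeks. Using 30 post-dose days instead gives 65 days, or 9.3 weeks.

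**The window.**
- Nominal length for a completer: 21 + 30 = 51 days; post-dose share 30/51 = 59%.
- The contact falls 19 to 23 days after the last dose, so 30 − 23 = 7 to 30 − 19 = 11 days lie beyond it (23% to 37% of the 30).
- Planned observation for non-rollover subjects is 21 + 19 = 40 to 21 + 23 = 44 days, with 19/40 = 48% to 23/44 = 52% post-dose. For rollover subjects it is about 21 days, with roughly none post-dose.

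The 59% is therefore an upper limit on the calendar, not the observation anyone receives. Because 30 exceeds 23, the limit never discards an event elicited at the planned contact.

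**Who gets the contact.** Protocol 3.1 and SAP 3.1 both say that subjects who do not enter the rollover are followed up, and then add early withdrawals. Footnote c agrees. Protocol 3.7.1.8 and the Synopsis restate the contact without repeating the limit. These shorter statements are not a competing rule.

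**If rollover events were counted here (all inputs assumed).** Open-label brexpiprazole starts at once, 21-day risks are 10% and 2%, 50% to 70% of each arm rolls over, and there are no further events in the others.
- Constant onset: h = −ln(0.90)/21 = 0.00502 per day. Rollover subjects over 51 days: brexpiprazole 1 − 0.90·exp(−30h) = 22.6%; placebo 1 − 0.98·exp(−30h) = 15.7%. At 50% rollover the arms show 16.3% and 8.8%, difference 7.4 points; at 70%, 18.8% and 11.6%, difference 7.2. The starting difference is 8.0.
- Onset only in the first 21 days of exposure: brexpiprazole stays at 10%. Placebo is 0.02 + 0.98·0.5·0.10 = 6.9% (difference 3.1) or, at 70%, 0.02 + 0.98·0.7·0.10 = 8.9% (difference 1.1). Reversal needs a rollover share above 0.08/(0.98·0.10) = 82%.

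**If rollover events stay in the rollover trial (risks and shares assumed).** Take 21-day risks of 10% and 5%, with non-rollover subjects observed for 21 further days at the placebo rate.
- No rollover: 1 − 0.90·0.95 = 14.5% and 1 − 0.95·0.95 = 9.75%; difference 4.75 points, ratio 1.49.
- Half of each arm rolls over and adds no post-dose days: the post-dose factor is 0.5 + 0.5·0.95 = 0.975. The arms show 1 − 0.90·0.975 = 12.25% and 1 − 0.95·0.975 = 7.375%; difference 4.9 points, ratio 1.66.

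On-treatment values are 5.0 points and 2.0. The difference barely moves. The ratio shrinks because both arms gain the same background events.

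**The case for a change.** The best case for a change is that label and content cannot both be right, and that neither reading gives a clean comparison. Protocol 3.1 and 3.7.1.7 foresee new medication after early termination, so events on other drugs can fall inside the window even if rollover events are held elsewhere. Rollover shares can also differ by arm. In the last illustration, 70% rollover on brexpiprazole and 50% on placebo gives 1 − 0.90·(0.7 + 0.3·0.95) = 11.35% against 7.375%, a difference of 4.0 points. Reversing the shares gives 12.25% against 1 − 0.95·0.985 = 6.4%, or 5.8 points. An extra table would cost little.

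The label point stands, as does the fact that post-dose observation depends on rollover status. Three things weaken the rest.
- The claim that the plan has no end rule and no split concerns text that cannot be seen. A redacted block follows the list of tables in SAP 9.1, SAP section 13 (the proposed list of tables) is blacked out, and the text of Protocol section 5 on adverse-event reporting is not in the copy available.
- Ending the window at the first open-label dose would not cure unequal follow-up, since rollover subjects already have no scheduled contact here after Day 21. The date of that dose belongs to another trial, and the visible schedule does not collect it.
- The 7-day rule in SAP 10.1 assigns scale ratings to visits. Adverse events carry their own onset dates, so it is not a precedent that section 9.1 breaks.

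**Conclusion.** No change to the plan is needed. Followed as written, SAP 9.1 yields an ordinary 30-day post-dose treatment-emergent table under a label that is too narrow. A longer window catches late-reported and delayed events at the price of including background events; a shorter one does the reverse. Reasonable statisticians differ on which to put first. Treatment-emergent status already rests on onset date, and SAP 10.1 already uses the last double-blind dosing date, so an analyst can tabulate on-treatment events from data in hand. A table footnote giving the window would settle the label.

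Contamination by open-label treatment is not shown. It would require events from a separate trial to enter this database, and no readable text says they do.

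The size rests on assumed risks and rollover shares. With rollover events held elsewhere and equal shares, the assumed 5.0-point difference becomes 4.75 to 4.9. A 20-point gap in rollover between the arms shifts it by about one point either way. The conclusion would weaken if unseen text showed that rollover events are merged into these tables. The primary and key secondary efficacy tests are unaffected in every case.

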## 9.2 Clinical Laboratory Tests

Summary statistics for mean and mean change from baseline in the routine clinical laboratory measurements, prolactin concentrations, coagulation parameters (PT, aPTT, and INR), HbA1c, and TSH will be provided by treatment and by visit.

Potentially clinically relevant laboratory measurement test results in the double-blind treatment period will be identified for the Safety Sample and will be summarized by treatment group and listed. Criteria for identifying laboratory values of potential clinical relevance are provided in [Appendix 2](#).

### 9.2.1 Drug Induced Liver Injury (DILI)

Total bilirubin level should be checked for any subject with increased ALT or AST levels  $\geq$  three times the upper normal limits (ULN) or baseline.

- Reporting all DILI as SAE to the FDA based on Hy's Law:
  - AST or ALT  $\geq$  3 x ULN or baseline and
  - T\_Bili  $\geq$  2 x ULN or baseline

SAP 331-201-00080

A separate incidence table will be provided for DILI cases, and the corresponding listing will be provided for Safety Sample during the double-blind treatment period.

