ALP = alkaline phosphatase; BUN = blood urea nitrogen; GGT = gamma glutamyl transferase; LDH = lactic dehydrogenase; MCHC = mean corpuscular hemoglobin concentration; RBC = red blood cell; WBC = white blood cell.

Any value outside the normal range will be flagged for the attention of the investigator who must indicate whether or not a flagged value is of clinical significance. If one or more values are questionable, the test(s) may be repeated. If the result of any test (or repeat test, if done) is indicated as clinically significant in the samples taken during the screening period, the subject will NOT be enrolled into the trial without the permission of the medical monitor. In addition, follow-up unscheduled laboratory tests should be performed if clinically significant abnormalities are observed. Unscheduled laboratory tests may be repeated at any time at the discretion of the investigator for appropriate medical care. Refer to [Appendix 3](#) for criteria for identifying values of potential clinical relevance.

The following laboratory test results at screening are exclusionary:

- Platelets $\leq 75000/\text{mm}^3$

Protocol 331-201-00080

- Hemoglobin \leq 9 g/dL
- Neutrophils, absolute \leq 1000/mm³
- Aspartate aminotransferase (AST) $> 2 \times$ upper limit of normal (ULN)
- Alanine aminotransferase (ALT) $> 2 \times$ ULN
- Creatine phosphokinase (CPK) $> 3 \times$ ULN, unless discussed with and approved by the medical monitor
- Creatinine \geq 2 mg/dL

The total volume of blood to be collected during the trial per subject is expected to be approximately 50 mL.

A pregnancy test will be conducted in WOCBP prior to trial intervention; results must be available prior to the administration of the IMP. Pregnancy tests can be performed at any point during the trial if pregnancy is suspected.

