Appendix 3**Criteria for Identifying Laboratory Values of Potential Clinical Relevance**

Laboratory Tests	Criteria
Chemistry	
AST (SGOT)	≥ 3 x upper limit of normal (ULN)
ALT (SGPT)	≥ 3 x ULN
Alkaline phosphatase	≥ 3 x ULN
LDH	≥ 3 x ULN
BUN	≥ 30 mg/dL
Creatinine	≥ 2.0 mg/dL
Uric Acid	
Men	≥ 10.5 mg/dL
Women	≥ 8.5 mg/dL
Bilirubin (total)	≥ 2.0 mg/dL
CPK	≥ 3 x ULN
Prolactin	> ULN
Hematology	
Hematocrit	
Men	≤ 37 % and decrease of ≥ 3 percentage points from baseline
Women	≤ 32 % and decrease of ≥ 3 percentage points from baseline
Hemoglobin	
Men	≤ 11.5 g/dL
Women	≤ 9.5 g/dL
White blood count	≤ 2,800/ mm ³ or ≥ 16,000/ mm ³
Eosinophils	≥ 10%
Neutrophils	≤ 15%
Absolute neutrophil count	≤ 1,000/ mm ³
Platelet count	≤ 75,000/ mm ³ or ≥ 700,000/ mm ³
Urinalysis	
Protein	Increase of ≥ 2 units
Glucose	Increase of ≥ 2 units
Casts	Increase of ≥ 2 units
Additional Criteria	
Chloride	≤ 90 mEq/L or ≥ 118 mEq/L
Potassium	≤ 2.5 mEq/L or ≥ 6.5 mEq/L
Sodium	≤ 126 mEq/L or ≥ 156 mEq/L
Calcium	≤ 8.2 mg/dL or ≥ 12 mg/dL
Glucose	
Fasting	≥ 100 mg/dL
Non-Fasting	≥ 200 mg/dL
Total Cholesterol, Fasting	≥ 240 mg/dL
LDL Cholesterol, Fasting	≥ 160 mg/dL
HDL Cholesterol, Fasting	
Men	< 40 mg/dL
Women	< 50 mg/dL
Triglycerides, Fasting	≥ 150 mg/dL

Protocol 331-201-00080

Appendix 4

Criteria for Identifying Electrocardiogram Measurements of Potential Clinical Relevance

Variable	Criterion Value ^a	Change Relative to Baseline ^a
Rate		
Tachycardia	≥ 120 bpm	increase of ≥ 15 bpm
Bradycardia	≤ 50 bpm	decrease of ≥ 15 bpm
Rhythm		
Sinus tachycardia ^b	≥ 120 bpm	increase of ≥ 15 bpm
Sinus bradycardia ^c	≤ 50 bpm	decrease of ≥ 15 bpm
Supraventricular premature beat	all	not present → present
Ventricular premature beat	all	not present → present
Supraventricular tachycardia	all	not present → present
Ventricular tachycardia	all	not present → present
Atrial fibrillation	all	not present → present
Atrial flutter	all	not present → present
Conduction		
1° atrioventricular block	PR ≥ 200 msec	increase of ≥ 50 msec
2° atrioventricular block	all	not present → present
3° atrioventricular block	all	not present → present
Left bundle-branch block	all	not present → present
Right bundle-branch block	all	not present → present
Pre-excitation syndrome	all	not present → present
Other intraventricular conduction block ^d	QRS ≥ 120 msec	increase of ≥ 20 msec
Infarction		
Acute or subacute	all	not present → present
Old	all	not present → present
		≥ 12 weeks post study entry
ST/T Morphological		

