**Appendix 2****Criteria for Identifying Laboratory Values of Potential Clinical Relevance**

Laboratory Tests	Criteria
Chemistry	
AST (SGOT)	$\geq 3 \times$ upper limit of normal (ULN)
ALT (SGPT)	$\geq 3 \times$ ULN
Alkaline phosphatase	$\geq 3 \times$ ULN
Lactate dehydrogenase (LDH)	$\geq 3 \times$ ULN
Blood urea nitrogen (BUN)	$\geq 30$ mg/dL
Creatinine	$\geq 2.0$ mg/dL
Uric Acid	
Men	$\geq 10.5$ mg/dL
Women	$\geq 8.5$ mg/dL
Bilirubin (total)	$\geq 2.0$ mg/dL
Creatine phosphokinase (CPK)	$\geq 3 \times$ ULN
Prolactin	$>$ ULN
Hematology	
Hematocrit	
Men	$\leq 37\%$ and decrease of $\geq 3$ percentage points from Baseline
Women	$\leq 32\%$ and decrease of $\geq 3$ percentage points from Baseline
Hemoglobin	
Men	$\leq 11.5$ g/dL
Women	$\leq 9.5$ g/dL
White blood count	$\leq 2,800/\text{mm}^3$ or $\geq 16,000/\text{mm}^3$
Eosinophils	$\geq 10\%$
Neutrophils	$\leq 15\%$
Absolute neutrophil count	$\leq 1,000/\text{mm}^3$
Platelet count	$\leq 75,000/\text{mm}^3$ or $\geq 700,000/\text{mm}^3$
Urinalysis	
Protein	Increase of $\geq 2$ units
Glucose	Increase of $\geq 2$ units
Casts	Increase of $\geq 2$ units
Additional Criteria	
Chloride	$\leq 90$ mEq/L or $\geq 118$ mEq/L
Potassium	$\leq 2.5$ mEq/L or $\geq 6.5$ mEq/L
Sodium	$\leq 126$ mEq/L or $\geq 156$ mEq/L
Calcium	$\leq 8.2$ mg/dL or $\geq 12$ mg/dL
Glucose	
Fasting	$\geq 100$ mg/dL
Non-Fasting	$\geq 200$ mg/dL
Total Cholesterol, Fasting	$\geq 240$ mg/dL
LDL Cholesterol, Fasting	$\geq 160$ mg/dL
HDL Cholesterol, Fasting	
Men	$< 40$ mg/dL
Women	$< 50$ mg/dL
Triglycerides, Fasting	$\geq 150$ mg/dL

SAP 331-201-00080

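### SAP 9.2.1 lets an unqualified baseline multiple stand in for the ULN multiple, so subjects below the ULN-based thresholds can be tabulated as Hy's Law DILI cases

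*SAP*

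**What the plan says.** SAP 9.2.1 introduces the rule with "Reporting all DILI as SAE to the FDA based on Hy's Law". It has two limbs, both required: AST or ALT at or above "3 x ULN or baseline and" total bilirubin at or above "2 x ULN or baseline". The sentence on when to check bilirubin uses the same ULN-or-baseline form. The rule then feeds an output: "A separate incidence table will be provided for DILI cases, and the corresponding listing will be provided for Safety Sample during the double-blind treatment period".

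Three other places bear on it:

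- SAP section 9 takes safety baseline as the last value before the first dose, whether normal or abnormal.
- SAP Appendix 2, which matches Protocol Appendix 3, judges AST and ALT against ULN alone ("≥ 3 x upper limit of normal (ULN") and total bilirubin against an absolute 2.0 mg/dL. Neither has a baseline alternative.
- Protocol 3.7.3.2 excludes subjects whose screening AST or ALT exceeds 2 x ULN, so a baseline between 1 and 2 x ULN is possible.

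SAP 9.2.1 does not say whether the higher or the lower reference governs, does not confine the baseline alternative to subjects with a raised baseline, and does not require the later value to exceed ULN.

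**The concern.** A baseline alternative in a liver rule is usually there for subjects who enter with raised values. Joined by a bare or, it does nothing for them. It acts only on subjects whose baseline is below ULN, and there it lowers the bar. A subject can then be counted under a Hy's Law label with one or both values short of the ULN multiple, and sometimes with both values normal.

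The stake is the case count in a table of rare events that is likely to be read case by case. With 160 subjects planned per arm, a single false case is 1/160 = 0.6% of an arm and could look like a signal. The primary efficacy result is not touched.

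**Working it through.** The SAP derives no figure from this rule, so there is none to reproduce. The check is on the logic, followed by a rough gauge of frequency.

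**Thresholds on the plain reading.** Let b be baseline and y the post-baseline value.

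- Enzyme: y ≥ 3 x ULN or y ≥ 3b, which is y ≥ 3 x min(ULN, b).
- Bilirubin: y ≥ 2 x ULN or y ≥ 2b, which is y ≥ 2 x min(ULN, b).

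If b ≥ ULN the minimum is ULN and the baseline term is idle. If b < ULN the threshold falls below the ULN multiple. A subject meeting both ULN multiples always qualifies, so an added subject must miss at least one of them.

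**When both later values can be normal.** This needs 3b ≤ ULN for the enzyme (b ≤ ULN/3) and 2b ≤ ULN for bilirubin (b ≤ ULN/2).

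**Example, assuming ULN 40 U/L for ALT and 1.2 mg/dL for bilirubin.** ALT goes from 12 to 36 and bilirubin from 0.4 to 0.8.

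- Baseline multiples: 3 x 12 = 36, met; 2 x 0.4 = 0.8, met. The subject is a DILI case.
- ULN multiples: 3 x 40 = 120, not met; 2 x 1.2 = 2.4, not met.
- Appendix 2: 36 is below 120 and 0.8 is below 2.0, so neither value is flagged.

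**Grid check in multiples of ULN, steps of 0.1.** Both baselines run from 0.1 to 2.0, post-baseline enzyme from 0.1 to 8.0 and post-baseline bilirubin from 0.1 to 5.0: 20 x 80 x 20 x 50 = 1,600,000 combinations. The counts are products of the qualifying enzyme pairs and bilirubin pairs.

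| Rule | Enzyme pairs x bilirubin pairs | Cases | Against ULN only |
|---|---|---|---|
| ULN multiples only | 1,020 x 620 | 632,400 | – |
| Plain reading | 1,155 x 710 | 820,050 | 187,650 added, 0 lost |
| Higher of ULN and baseline | 855 x 510 | 436,050 | 0 added, 196,350 removed |

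Of the 187,650 added, none has both baselines at or above ULN, and 15 x 25 = 375 have both later values at or below ULN. These counts verify the logic. They are not frequencies in patients.

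**Frequency from random variation alone.** The documents give no liver-test distribution, so all inputs are assumed: one enzyme; median baseline 0.5 x ULN for the enzyme and 0.4 x ULN for bilirubin; between-subject SD 0.4 on the log scale; one post-baseline draw (the protocol schedule has chemistry only at screening and Day 21/ET); analytes independent; 4,000,000 simulated subjects.

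| Within-subject CV | Plain reading, cases per 320 | ULN only, cases per 320 | Share of plain-reading cases with both values normal |
|---|---|---|---|
| 20% | 0.0002 | 0 | 0% |
| 30% | 0.06 | 0.0001 | 50% |
| 40% | 0.73 | 0.0006 | 42% |

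The SAP accepts either AST or ALT. If both behave like the modelled enzyme, the count is at most doubled: 2 x 0.73 = 1.5 at CV 40%.

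**The case against.** The best reply is that the rule is deliberately over-sensitive. It cannot drop a ULN-based case, a listing lets each case be checked, and with one scheduled post-baseline draw the expected number of chance cases is close to nil over much of the assumed range. All of that stands, and it limits the size of the point. It does not remove it: an over-sensitive screen can sit on its own line, whereas here its cases carry the same Hy's Law label as the ULN-based ones.

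A reader might infer more than the documents support:

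- **That normal liver values would routinely be counted.** Both values being normal is a special case that needs low baselines plus a tripling and a doubling together. One sub-threshold analyte is enough to be an added case, and the other may be well above its ULN multiple.
- **That the rule hides true cases.** On the plain reading none is lost.
- **That subjects with raised baselines face a bar of up to 6 x ULN** (3 x the entry limit of 2 x ULN). That belongs to the higher-of reading, which the SAP does not state. Under it no case would be added and the point above would fall, but cases would be removed instead.
- **That Appendix 2 is wrong.** It flags single analytes, is taken from the protocol and serves another purpose.

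One further limit: Protocol section 5.4, on potential serious hepatotoxicity, appears by title in the contents, but its text is not in the copy reviewed. It may set the same trigger.

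**Conclusion.** The point holds as a defect in a tabulation rule. Followed as written, SAP 9.2.1 puts into the DILI table subjects who miss at least one ULN-based threshold, and in the low-baseline case subjects with wholly normal values whom Appendix 2 would not flag (provided the bilirubin ULN is below 2.0 mg/dL). It adds nothing when both baselines are at or above ULN.

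The algebra needs no assumption beyond reading the or as it stands. The number of cases does depend on assumptions: it is unknown from the documents and probably small, from essentially none to about 0.7 per 320 subjects for one enzyme, or at most about 1.5 for two. The wording needs settling on either intention, because the plain and higher-of readings move the count in opposite directions and a programmer cannot tell which applies.

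**What to change.** In SAP 9.2.1, define the DILI incidence table and listing on ULN multiples: AST or ALT at least 3 x ULN and total bilirubin at least 2 x ULN. If a baseline multiple is wanted, show it as a separate, labelled descriptive line that states when baseline is the reference. Appendix 2 need not change.

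The SAE-reporting and bilirubin-check sentences are a different matter. The sponsor should reconcile their wording with Protocol section 5.4; no reporting threshold is proposed here.

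The cost is a short change to the SAP text and one extra table line. Fewer low-level rises appear under the DILI heading, but they remain visible on the separate line.
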